### **6.3.3. Safety Population**

The Safety Analysis population includes all pregnant women who received the study vaccination, and all infants born during the study.

### **6.3.4. Immunogenicity Population**

The immunogenicity population will be the ITT population and PP population as described in [Section 6.3.1](#) and [Section 6.3.2](#).

## **6.4. Covariates and Subgroups**

This study is not powered for formal subgroup analyses; however, immunogenicity subgroups will be explored.

To evaluate the association with maternal immunogenicity cofactors, maternal and infant anti-PT ELISA response will be summarized stratified by maternal age (18-29, 30-39 years old), parity (primiparous vs. multiparous), GA at time of vaccination (14-17, 18-21, 22-26 weeks), GA at time of delivery (28-32, 33-36, 37 or more weeks), and infant birthweight. These cofactors will be evaluated in regression modeling.

## **6.5. Missing Data and Outliers**

All attempts will be made to collect all data per protocol. As missing data are expected to be minimal, no imputation will be performed for missing values. Any data point that appears to be erroneous or inexplicable based on clinical judgment will be investigated as a possible outlier. If data points are identified as outliers, sensitivity analyses will be performed to examine the impact of including or excluding the outliers. Any substantive differences in these analyses will be reported.

## **6.6. Interim Analyses and Data Monitoring**

Interim analyses would only be used to terminate this trial in the event that unanticipated safety events deemed to be of sufficient concern to require such action by the sponsor. A DSMB will be convened by DMID to review study progress and subject, clinical, safety, and reactogenicity data.

Cumulative safety information, study status, and primary endpoint results may be presented at a public forum in a blinded manner or presented as summaries aggregated by study arm at the discretion of the sponsor while the primary study is ongoing. While the primary study is ongoing no data will be released that is unblinding at an individual subject level, and caution will be taken to ensure that data summarized by treatment arm does not identify the treatment assignment of any individual subject. Any ad-hoc analyses, jointly developed by the SDCC and/or University of Maryland, will be executed by the SDCC as needed. None of the interim analyses will include any formal statistical hypothesis testing; therefore, pvalue adjustment will not be made to any analyses

An interim safety review will occur when safety data collected through Day 8 is available for 25% of pregnant study subjects. Reports for interim safety reviews will include data for pregnant participants, and any infants born at the time of data cutoff. Summaries may include enrollment and demographic information, medical history, concomitant medications, physical assessments, and solicited and unsolicited AE/SAEs. Additional data may be requested by the DSMB. This trial will be monitored to determine if any of the halting rules are met.

An interim immunogenicity review is not planned.

## **6.7. Multicenter Studies**

Not applicable. This study will take place at a single VTEU site in Mali.

## **6.8. Multiple Comparisons/Multiplicity**

This study was not designed to test any specific null hypothesis, and as such no adjustments for multiple testing are planned.

## 7. STUDY SUBJECTS

### 7.1. Disposition of Subjects

[Table 14](#) will present a summary of the reasons that subjects were screened but not enrolled.

The composition of analysis populations, including reasons for subject exclusion, by treatment arm, is presented in [Table 11](#) for maternal subjects and [Table 12](#) for infant subjects.

The disposition of subjects in the study will be tabulated by treatment group ([Table 9](#) and [Table 10](#)). [Table 9](#) shows the total number of maternal subjects screened, enrolled, receiving treatment, and completing the study. [Table 10](#) shows the number of infant subjects enrolled, completing the birth visit blood draw, and completing the study.

A flowchart showing the disposition of study subjects, adapted from the Consort Statement [12] will be included ([Figure 2](#)). This figure will present the number of subjects screened, enrolled, lost to follow-up, and analyzed, by treatment arm.

A listing of subjects who terminated from study follow-up and the reason will be included in [Listing 1](#).

### 7.2. Protocol Deviations

A summary of subject-specific protocol deviations will be presented by the reason for the deviation, the deviation category, and treatment group for all enrolled mothers and infants ([Table 6](#) and [Table 7](#), respectively). Deviations that are considered major deviations that will be reviewed for possible subject exclusion from the per protocol population include: mother receipt of non-study licensed vaccine, mother receipt of immunosuppressive therapy, infant did not receive DTwP within window, infant received product that would impact immune response and infant blood samples captured substantially out of window. All subject-specific protocol deviations and non-subject specific protocol deviations will be included in [Appendix 3](#) as data listings ([Listing 2](#) and [Listing 3](#), respectively).

## 8. IMMUNOGENICITY EVALUATION

This study was not designed to test a specific null hypothesis, rather the primary objectives included assessing the safety and tolerability of BOOSTRIX compared to Td and assessing infant humoral immunity between maternal subjects that received BOOSTRIX or Td.

Immunogenicity data summaries and analysis for maternal subjects will be presented for the maternal ITT and the maternal PP populations. Immunogenicity data summaries and analysis for infants will be presented for the infant ITT and infant PP populations.

[Listing 8](#) (antibody) and [Listing 9](#) (cytokine) will present individual immunogenicity results.

### 8.1. Primary Immunogenicity Analysis

The primary immunogenicity analysis will assess the level of PT antibody at birth among infants whose mothers received a single dose of BOOSTRIX or Td while pregnant. Summaries and analysis of serum IgG antibody concentrations to PT at birth will be presented. Analysis will include GMCs along with corresponding 95% confidence intervals. The GMC between treatment groups will be compared using a t-test on log-transformed ELISA titers ([Table 21](#) and [Table 22](#)).

Reverse cumulative distributions (RCD) curves will be presented for serum IgG antibody concentrations to PT. Plots will be generated with two panels (Birth and Prior to Receipt of First dose of DTwP), and separate curves within each panel for each treatment group, as shown in [Figure 3](#) and [Figure 4](#). Log-transformed serum IgG antibodies to PT will be plotted by treatment group along with the geometric mean ([Figure 57](#) and [Figure 58](#)). The GMCs and 95% confidence intervals of log-transformed serum IgG antibodies to PT will be plotted with panels for each treatment group ([Figure 111](#) and [Figure 112](#)).

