7.3. Enrollment/Baseline

Enrollment and Vaccination Visit, Day 1: Clinic Visit, Pregnant Women (Visit 01 or V01)

- Reconfirm subject's willingness to participate prior to performing any study procedures, including administration of the study vaccination.
- Obtain informed consent (if screening and enrollment visits have been combined).
- Review eligibility criteria with subjects prior to the study vaccination to ensure eligibility.
- Complete medical history and any updates obtained by interview and/or review of medical charts of subjects since the screening visit will be reviewed with subjects prior to the study vaccination to ensure eligibility.
- All concomitant medications and vaccinations will be reviewed with subjects prior to the study vaccination for accuracy and completeness. Any new concomitant medications/vaccinations taken since the screening visit will be reviewed with subjects and used in the assessment for eligibility, prior to the study vaccination. Medications reported in the eCRF are limited to those taken within 30 days prior to the study vaccination. Subjects will be reminded they should not plan to receive any live or inactivated vaccine within 30 or 14 days, respectively, after study vaccination.
- Vital signs, namely oral temperature, pulse, and blood pressure, will be obtained prior to the study vaccination. Vital signs assessed on Day 1 prior to the study vaccination will be considered as baseline. Subjects will be asked not to eat or drink anything hot or cold, or smoke within 10 minutes prior to taking an oral temperature.

- Height and weight will be obtained, if not done on screening visit.
- A targeted physical examination may be performed prior to the study vaccination by a study clinician licensed to make medical diagnoses and listed on the Form FDA 1572 as the site principal investigator or sub-investigator, if indicated based on review of complete medical history and any updates obtained by interview of subjects or medical chart review since the screening visit. For pregnant women, an examination performed by her own obstetrical clinician may also provide data when a targeted exam is called for.
- Approximately 30 mL of venous blood will be collected immediately prior to the study vaccination for baseline serology and cytokine assays.
- Subjects will be enrolled in Advantage eClinical and assigned to treatment arm (BOOSTRIX or Td) and post-partum study schedule.

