#### 6.3.2. Per Protocol (PP) Population

The maternal per-protocol (PP) population for immunogenicity analyses includes all subjects in the ITT subset with the following exclusions:

- Data from all available visits for subjects:
  - Found to be ineligible at baseline.
  - Without results from the baseline visits.
  - Without results from at least one post-vaccination visit.
- Data from all visits subsequent to major protocol deviations, such as:
  - Receipt of non-study licensed vaccine within the pre-specified exclusion windows ([Section 4.3.2](#)).

- Receipt of immunosuppressive therapy (e.g., corticosteroids) within 30 days prior to or after study vaccination.
- Data from any visit that occurs substantially out of window.

The infant PP population for *primary and secondary* immunogenicity analyses includes all infants in the ITT subset who have a blood sample from the perinatal period (cord blood or drawn blood within the 72 hours after birth).

The infant PP population for *exploratory* immunogenicity analyses includes all infants in the ITT subset with the following exclusions:

- Infants who did not receive DTwP within appropriate window.
- Infants who received any product that would impact immune response.
- Infants with blood samples captured substantially out of window.

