The models will be produced using PROC GLM or equivalent in SAS. All assumptions for regression models will be assessed by viewing diagnostic plots such as residual plots and QQ plots. The sample sizes, parameter estimates, and parameter standard errors will be presented in [Table 41](#), [Table 42](#), [Table 43](#), and [Table 44](#). For the analysis of variance models of categorical cofactors, the ratio of the GMC of each non-reference level with respect to the GMCs of the reference level will be computed and displayed along with the 95% confidence interval. These values are calculated by exponentiating the level-specific parameter estimate  $\hat{\beta}_{1i}$  and its 95% confidence interval.

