## 14.2 Immunogenicity Data

**Table 21: Serum IgG ELISA Geometric Mean Concentration (GMC) Results with 95% Confidence Intervals by Antigen, Time Point, and Treatment Group -- Infant Intent-to-Treat Population**

Tdap Antigen	Time Point	Statistic	BOOSTRIX (N=X)	Td (N=X)	Difference
Pertussis Toxin (PT)					
	Birth	n	x	x	--
		GMC (95% CI)	x.x (x.x, x.x)	x.x (x.x, x.x)	x.x (x.x, x.x)
		p-value*	--	--	0.xxx
	Prior to receipt of first dose of DTwP (approximately 6 weeks of age)	n			
		GMC (95% CI)			
		p-value*			
Filamentous Hemagglutinin (FHA)					
	Birth	n			
		GMC (95% CI)			
		p-value*			
	Prior to receipt of first dose of DTwP (approximately 6 weeks of age)	n			
		GMC (95% CI)			
		p-value*			
Pertactin (PRN)					
	Birth	n			
		GMC (95% CI)			
		p-value*			
	Prior to receipt of first dose of DTwP (approximately 6 weeks of age)	n			
		GMC (95% CI)			
		p-value*			
Tetanus					
	Birth	n			
		GMC (95% CI)			

Table 21: Serum IgG ELISA Geometric Mean Concentration (GMC) Results with 95% Confidence Intervals by Antigen, Time Point, and Treatment Group -- Infant Intent-to-Treat Population (continued)

Tdap Antigen	Time Point	Statistic	BOOSTRIX (N=X)	Td (N=X)	Difference
		p-value*			
	Prior to receipt of first dose of DTwP (approximately 6 weeks of age)	n			
		GMC (95% CI)			
		p-value*			
Diphtheria					
	Birth	n			
		GMC (95% CI)			
		p-value*			
	Prior to receipt of first dose of DTwP (approximately 6 weeks of age)	n			
		GMC (95% CI)			
		p-value*			
Note: N=Number of subjects in the Infant ITT Population n=Number of subjects with results available at time point *p-value is based on t-test on log-transformed ELISA titers.					

Table with similar format:

**Table 22: Serum IgG ELISA Geometric Mean Concentration (GMC) Results with 95% Confidence Intervals by Antigen, Time Point, and Treatment Group -- Infant Per Protocol Population**

**Table 23: ELISA Geometric Mean Concentration (GMC) Results of Antibodies to DTwP Antigens with 95% Confidence Intervals by Antigen, Time Point, and Treatment Group -- Infant Intent-to-Treat Population**

DTwP Antigen	Time Point	Statistic	BOOSTRIX (N=X)	Td (N=X)	Difference
Pertussis Toxin (PT)					
	One month after receipt of first dose of DTwP (approximately 10 weeks of age)	n	x	x	--
		GMC (95% CI)	x.x (x.x, x.x)	x.x (x.x, x.x)	x.x (x.x, x.x)
		p-value*	--	--	0.xxx

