	One month after receipt of first dose of DTwP (approximately 10 weeks of age)	n			
		GMC (95% CI)			
		p-value*			
	One month after receipt of last dose of DTwP (approximately 18 weeks of age)	n			
		GMC (95% CI)			
		p-value*			
	At 6 months of age	n			
		GMC (95% CI)			
		p-value*			
Note: N=Number of subjects in the Infant ITT Population n=Number of subjects with results available at time point *p-value is based on t-test on log-transformed ELISA titers.					

Table with similar format:

**Table 24: ELISA Geometric Mean Concentration (GMC) Results of Antibodies to DTwP Antigens with 95% Confidence Intervals by Antigen, Time Point, and Treatment Group -- Infant Per Protocol Population**

**Table 25: Serum IgG ELISA Geometric Mean Concentration (GMC) Results with 95% Confidence Intervals by Antigen, Time Point, and Treatment Group -- Maternal Intent-to-Treat Population**

Antigen	Time Point	Statistic	BOOSTRIX (N=X)	Td (N=X)	Difference
Pertussis Toxin (PT)					
	One month after vaccination	n	x	x	--
		GMC (95% CI)	x.x (x.x, x.x)	x.x (x.x, x.x)	x.x (x.x, x.x)
		p-value*	--	--	0.xxx
	At delivery	n			
		GMC (95% CI)			
		p-value*			
	6 months after delivery	n			
		GMC (95% CI)			
		p-value*			
Filamentous Hemagglutinin (FHA)					
	One month after vaccination	n			
		GMC (95% CI)			
		p-value*			
	At delivery	n			
		GMC (95% CI)			
		p-value*			
	6 months after delivery	n			
		GMC (95% CI)			
		p-value*			
Pertactin (PRN)					
	One month after vaccination	n			
		GMC (95% CI)			
		p-value*			
	At delivery	n			
		GMC (95% CI)			
		p-value*			
	6 months after delivery	n			

Table 25: Serum IgG ELISA Geometric Mean Concentration (GMC) Results with 95% Confidence Intervals by Antigen, Time Point, and Treatment Group -- Maternal Intent-to-Treat Population (continued)

Antigen	Time Point	Statistic	BOOSTRIX (N=X)	Td (N=X)	Difference
		GMC (95% CI)			
		p-value*			
Tetanus					
	One month after vaccination	n			
		GMC (95% CI)			
		p-value*			
	At delivery	n			
		GMC (95% CI)			
		p-value*			
	6 months after delivery	n			
		GMC (95% CI)			
		p-value*			
Diphtheria					
	One month after vaccination	n			
		GMC (95% CI)			
		p-value*			
	At delivery	n			
		GMC (95% CI)			
		p-value*			
	6 months after delivery	n			
		GMC (95% CI)			
		p-value*			

Note: N=Number of subjects in the Maternal ITT Population  

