n=Number of subjects with results available at time point  
\*p-value is based on t-test on log-transformed ELISA titers.

Table with similar format:

Table 26: Serum IgG ELISA Geometric Mean Concentration (GMC) Results with 95% Confidence Intervals by Antigen, Time Point, and Treatment Group -- Maternal Per Protocol Population

**Table 27: Geometric Mean Ratio (GMR) of Maternal and Infant-Specific Tdap-Specific Antibodies as Measured by ELISA with 95% Confidence Intervals by Antigen and Treatment Group -- Intent-to-Treat Population**

Antigen	Statistic	BOOSTRIX	Td
Pertussis Toxin (PT)	N	x	x
	GMR a (95% CI)	x.x (x.x, x.x)	x.x (x.x, x.x)
Filamentous Hemagglutinin (FHA)	N		
	GMR a (95% CI)		
Pertactin (PRN)	N		
	GMR a (95% CI)		
Tetanus	N		
	GMR a (95% CI)		
Diphtheria	N		
	GMR a (95% CI)		

Note: N=Number of mother infant pairs in the intent-to-treat population with antibody levels available at delivery/birth.  
a GMR represents the geometric mean ratio in maternal antibody concentration at delivery to infant antibody concentration at birth.

Table with similar format:

**Table 28: Geometric Mean Ratio (GMR) of Maternal and Infant-Specific Tdap-Specific Antibodies as Measured by ELISA with 95% Confidence Intervals by Antigen and Treatment Group -- Per Protocol Population**

**Table 29: Breast Milk IgG ELISA Geometric Mean Concentration (GMC) Results with 95% Confidence Intervals by Antigen, Time Point, and Treatment Group -- Maternal Intent-to-Treat Population**

Antigen	Time Point	Statistic	BOOSTRIX (N=X)	Td (N=X)	Difference
Pertussis Toxin (PT)					
	At delivery	n	x	x	--
		GMC (95% CI)	x.x (x.x, x.x)	x.x (x.x, x.x)	x.x
		p-value*	--	--	0.xxx
	6 weeks after delivery	n			
		GMC (95% CI)			
		p-value*			
	10 weeks after delivery	n			
		GMC (95% CI)			
		p-value*			
	18 weeks after delivery	n			
		GMC (95% CI)			
		p-value*			
	6 months after delivery	n			
		GMC (95% CI)			
		p-value*			
Filamentous Hemagglutin (FHA)					
	At delivery	n			
		GMC (95% CI)			
		p-value*			
	6 weeks after delivery	n			
		GMC (95% CI)			
		p-value*			
	10 weeks after delivery	n			
		GMC (95% CI)			
		p-value*			
	18 weeks after delivery	n			

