**16.2.6 Individual Immunogenicity Response Data****Listing 8: 16.2.6: Individual Immunogenicity Response Data (Antibody)**

Treatment Group	Subject ID	Maternal/Infant	Planned Time Point	Actual Study Day	Tdap/DTwP	Serum IgG/Serum IgA/Breast Milk	Antibody Tested	Titer

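### Cheap improvement, not an error: report the between-arm contrast as a BOOSTRIX/Td GMC ratio with a Welch CI, and add a supplementary analysis adjusted for maternal Day 1 antibody

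*SAP*

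**What the plan says.** SAP 8.1 plans arm GMCs with 95% CIs and then: "The GMC between treatment groups will be compared using a t-test on log-transformed ELISA titers". SAP 8.2.1, 8.2.2, 8.2.4 and 8.3.2 repeat this for the other antibody endpoints, and Protocol 11.4.3 names the same test. None of them specifies the pooled or the Welch form.

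The shells for SAP Tables 21, 23 and 25 have a column headed Difference with room for a CI. The footnote defines only the p-value: "p-value is based on t-test on log-transformed ELISA titers". Tables 22, 24 and 26 copy the format. Table 29 is titled "Breast Milk IgG ELISA Geometric Mean Concentration (GMC) Results with 95% Confidence Intervals by Antigen, Time Point, and Treatment Group", and its row label also promises a CI, but its Difference cell shows a single value; Tables 30-32 follow it. For the exploratory cofactors, by contrast, SAP 8.3.1 says "the ratio of the GMC of each non-reference level with respect to the GMCs of the reference level will be computed and displayed" with a 95% CI obtained by exponentiating.

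On baseline antibody, Protocol 7.3 says: "Approximately 30 mL of venous blood will be collected immediately prior to the study vaccination for baseline serology and cytokine assays". SAP 6.3.2 removes from the maternal per-protocol set women "Without results from the baseline visits". SAP 4.5.2, SAP 8.2.1 and Table 25 ("Serum IgG ELISA Geometric Mean Concentration (GMC) Results with 95% Confidence Intervals by Antigen, Time Point, and Treatment Group -- Maternal Intent-to-Treat Population") nevertheless list maternal serum antibody only at one month after vaccination, delivery and 6 months after delivery. Day 1 titers might appear in Listing 8 ("Individual Immunogenicity Response Data (Antibody") or under the broad Protocol 11.4.3 wording on reporting by time point, but no stated between-arm analysis uses them. Maternal cytokines do get Day 1 values and change (SAP 8.3.3).

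**The concern.** A t-test on log titers compares mean logs, and its back-transformed contrast is a GMC ratio. If the programmer fills the column with an arithmetic difference of GMCs, the estimate and the p-value will be on different scales, and the planned test supplies no CI for that estimate. The study is meant to give preliminary estimates (Protocol 11.1), so the contrast and its CI are the main product of the primary table.

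The unstated variance form also matters. With twice as many women on BOOSTRIX, a pooled t-test rejects too often if Td titers are the more variable, and the documents give no Td-arm SD for PT at birth.

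The Day 1 draw is a baseline measurement the trial already pays for. If it predicts later titers, adjusting for it narrows the between-arm CI. A link is plausible: infant antibody comes across the placenta (Protocol 2.1.3), and Td contains no pertussis antigen (Protocol 6.1.2), so PT antibody at birth in the Td arm should largely reflect what the mother already had. The documents do not quantify it.

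**Working it through.** **Inputs.** Enrollment is 133 BOOSTRIX and 67 Td. Up to 15% may be lost to the per-protocol analysis (Protocol 11.2.2), which leaves 0.85 × 133 ≈ 113 and 0.85 × 67 ≈ 57. The log-SD for infant PT at birth after Tdap is 0.78 (Protocol Table 10, SAP Table 4). The example GMCs of 70.0 and 44.7 are one row of Protocol Table 11 (SAP Table 5). The correlation r between log maternal Day 1 titer and log outcome is assumed.

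**Plan's own figure.** Table 10 gives infant PT at N = 133 as 68.8 (60.2 to 78.7). Recomputed as 68.8 × exp(± t × 0.78/√133), it is 60.2 to 78.6, which agrees to rounding. So 0.78 is a natural-log SD.

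**Ratio, unadjusted (pooled, equal SDs).**
- ln(70/44.7) = 0.4485, ratio 1.57.
- SE = 0.78 × √(1/113 + 1/57) = 0.78 × 0.1625 = 0.1267.
- Half-width = t(0.975, 168) × SE = 1.974 × 0.1267 = 0.2502.
- 95% CI = exp(0.4485 ± 0.2502) = 1.22 to 2.01.

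**Ratio, adjusted.** Multiply the SE by √(1 − r²) and use 167 df.
- r = 0.3: half-width 0.2387, CI 1.23 to 1.99.
- r = 0.5: half-width 0.2167, CI 1.26 to 1.94 (upper limit 1.945 before rounding).

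The GMC pair is only an illustration. Its Table 11 row implies a log-SD of 1.06 at 80% power, and the five rows imply values from 0.94 to 1.14, so that table is not a reliable source for an SD.

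**Pooled or Welch.** By simulation at 133/67 with log-SD 0.78 in both arms, both forms have type I error near 5%. With an assumed Td log-SD of 1.1, the pooled test rejects in about 7.8% of trials and Welch in about 5%.

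**Adjustment with robust standard errors.** Each case used 20,000 simulated trials at 113/57 with normal data, equal outcome SDs and no true effect. The model was arm plus baseline, one common slope, HC3 (heteroscedasticity-robust) standard errors. Log-scale CI width relative to the pooled t-test:

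| r, BOOSTRIX / Td | Relative width |
|---|---|
| 0 / 0 | 1.01 |
| 0.3 / 0.3 | 0.97 |
| 0.5 / 0.5 | 0.88 |
| 0.1 / 0.5 | 0.95 |
| 0.2 / 0.8 | 0.84 |
| 0.6 / 0 | 1.01 |
| 0.5 / −0.2 | 1.04 |

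In the four unequal-slope cases, coverage of the 95% CI was 95.0-95.2%. Ordinary standard errors gave 92.9% and 93.4% in the last two cases, and adding an arm-by-baseline term with HC3 gave 94.2% and 93.8%. This is why a common slope with HC3 is proposed.

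**Missing or below-limit baselines.** With an assumed 10% of baselines missing and mean-imputed, the width was 0.97 at r = 0.3 and 0.89 at r = 0.5. With an assumed 40% below the assay limit and set to half the limit, it was 0.97 and 0.90. Coverage stayed at 95.2-95.5%.

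**The case against.** The plan already reports each arm's GMC with a CI, so the ratio is one division away, and a careful reader could approximate its CI. The trial tests no formal hypothesis (SAP 6.8). That stands, and it limits the first part to labeling and a stated method. It does not remove the ambiguity in the primary table.

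The adjustment rests on an undocumented correlation. That also stands. At log-SD 0.78 and r = 0.3 the CI moves only from 1.22-2.01 to 1.23-1.99. The biological argument is strongest in the Td arm, one third of the women, and unequal slopes can make the CI slightly wider. Because the t-test is the only between-arm antibody test the protocol names, adjustment belongs beside it and should not displace it.

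A reader might infer that Table 29 deliberately drops the CI. Its title and row label promise one, so an unfinished cell is equally likely. A reader might also infer that Difference means an arithmetic subtraction, since Table 11 uses BOOSTRIX minus Td. The antibody shells do not say so, and a log difference is not excluded.

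Finally, no rule is given for outcome titers below the assay limit, and the ratio depends on one. That is true, but the arm GMCs already planned depend on it equally.

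**Conclusion.** The point holds as a low-cost improvement in two parts.

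The ratio is worth reporting whatever r is, because it puts the estimate, CI and p-value on one scale. The Welch form protects against unequal arm SDs; the size of that risk (about 7.8% against 5%) rests on an assumed Td SD.

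The adjustment is a worthwhile supplement of uncertain value. Relative to the pooled t-test with equal SDs, its CI is about 1% wider at r = 0, 3% narrower at r = 0.3, 12% narrower at r = 0.5, and about 4% wider in the worst unequal-slope case tried.

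A reader might go further and conclude that the planned t-test is biased or wrong, or that an adjusted model should become primary. The documents support neither: randomization justifies the unadjusted comparison, the protocol specifies it, and nothing shows how strongly Day 1 antibody predicts the outcome. Nor is Day 1 ELISA a ready-made SAP variable. The blood draw is planned and baseline results are presumed, but SAP 4.5.2 does not list it.

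**What to change.** **Ratio.** In SAP Tables 21-26 and 29-32 replace Difference with the BOOSTRIX/Td GMC ratio and its back-transformed 95% CI, including the CI missing from the Table 29 cell. State in SAP 8.1 and the parallel sections that both CI and p-value use the Welch t-test. This costs shell and wording edits only; Welch is still the t-test that Protocol 11.4.3 names.

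**Day 1 antibody.** List maternal Day 1 ELISA in SAP 4.5.2 and add Day 1 GMCs to Tables 25 and 26.

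**Supplementary analysis.** Before unblinding, pre-specify for maternal serum time points and for infants at birth and 6 weeks: log(titer) = arm + log(maternal Day 1 titer, same antigen), one common slope, HC3 standard errors. Keep the protocol's t-test as primary. State a rule for missing and below-limit baselines so that no infant with a birth titer is dropped, for example the pooled mean for a missing covariate and half the limit for a low one. Imputing the covariate needs a stated exception to the no-imputation rule in SAP 6.5 and Protocol 11.4.4. The rest is minor programming.
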